4 STUDY DESIGN AND DOSE RATIONALE

4.1 Overall Study Design

This will be a randomized, participant- and investigator-blinded, placebo-controlled, single sequence study comprising of male and female recreational opioid-using participants.

Approximately 24 male and female participants will be randomly assigned to complete at least 18 participants. An attempt will be made to enroll 1 female participant for every 3 male participants. The study will be conducted at 1 study site in the US.

Participants will be screened for up to 28 days prior to first investigational product (IP) administration. Eligible participants will be admitted to the clinical unit on day -1 and will be residential for a single period of 17 days/16 nights. After randomization, participants will receive multiple oral doses of ASP8062 or placebo (2:1 ratio) on days 1 through 10. On day 10, all participants will also receive a single oral dose of morphine immediately after the ASP8062 or placebo dose followed by a 144-hour in-house blood sampling period.

Scheduled safety and tolerability assessments will be conducted as indicated in the Schedule of Assessments [Table 1]. Participants are to remain awake, seated or semirecumbent and avoid lying on either the left or right side for at least 4 hours postdose on days 9 and 10.

Participants will be discharged from the clinical unit on day 16 on the condition that all required assessments have been performed and that there are no medical reasons for a longer stay in the clinical unit.

The study will be completed with an end-of-study visit (ESV). The ESV will take place 5 to 9 days after the day 16 pharmacokinetic sample is collected or at early discontinuation/termination from the study.

4.2 Scientific Rationale for Study Design

A randomized, participant- and investigator-blinded, placebo-controlled, single sequence study was chosen to assess the safety and tolerability of multiple doses of ASP8062 alone and ASP8062 in combination with a single dose of morphine sulfate, a full μ -opioid receptor agonist. Participants will be randomized to treatment to reduce selection bias. Participants and the investigator will both be blinded to treatment to reduce bias in the measurement of the primary safety endpoints. Given the long pharmacokinetic $t_{1/2}$ of ASP8062 (approximately 60 hours), a single sequence study was chosen.

4.3 Dose Rationale

The primary objective of this study is to assess the safety and tolerability of multiple doses of ASP8062 alone and ASP8062 in combination with a single dose of morphine sulfate, a full μ -opioid receptor agonist. In the 8062-CL-0005 study, the AUCs of 30 mg ASP8062 with tablet B formulation (provided as a 30 mg tablet) were approximately 10% higher than 30 mg ASP8062 with tablet A formulation (provided as a 25 mg tablet plus a 5 mg tablet) with the 90% CI within the standard bioequivalence limits (80.00, 125.00); C_{max} was approximately 60% higher. With this finding, multiple doses of 25 mg ASP8062 with tablet B formulation will be proposed for future clinical studies for OUD. The predicted exposures after multiple

doses of 25 mg ASP8062 are 1828 h•ng/mL for AUC₂₄ and 143 ng/mL for C_{max}. These exposures will be comparable to exposures in the previous clinical studies and will not exceed mean exposure limit set in previous phase 1 studies (247 ng/mL for C_{max} and 2339 h•ng/mL for AUC₂₄); which means exposures achieved in this study are expected to be pharmacologically active (as seen in 8062-CL-0003) and also safe and tolerated based on data from previous clinical studies in a total of 137 healthy participants and 95 fibromyalgia patients.

The single dose of 45 mg morphine sulfate is 1.5 times higher than the approved highest individual dose per package insert [Morphine Sulfate Package Insert]. This dose is equivalent to 30 mg oxycodone, which is 2 times higher than the recommended highest individual dose and considered to be sufficient to show a sign of μ -receptor agonism. C_{max} after a single dose of 45 mg morphine sulfate immediate-release tablet is expected to be close to the reported maximum serum morphine concentration after intramuscular administration of morphine chloride (0.15 mg/kg body weight) in which most participants showed depression of the ventilatory response, characterized by the slopes of the carbon dioxide tension ventilation curves [Møller et al, 1982].

4.4 End of Study Definition

The end of the study is defined as the last visit or scheduled procedure shown in Schedule of Assessments [Table 1] for the last participant in the study.

5 STUDY POPULATION

All screening assessments must be completed and reviewed to confirm the potential participant meets all eligibility criteria. Prospective approval of protocol deviations to eligibility criteria (also known as protocol waivers or exemptions) is not permitted.

The study population will consist of male and female participants (18 to 60 years of age, inclusive) who have at least 10 lifetime uses of a recreational opioid drug with at least 1 opioid use in the last 90 days.

5.1 Inclusion Criteria

Participant is eligible for participation in the study if all of the following apply:

1. Institutional Review Board (IRB)/Independent Ethics Committee (IEC)-approved written informed consent and privacy language as per national regulations (e.g., Health Insurance Portability and Accountability Act authorization for US sites) must be obtained from the participant prior to any study-related procedures (including withdrawal of prohibited medication, if applicable).
2. Participant is a male or female participant between 18 to 60 years of age, inclusive at screening.
3. Participant is a recreational opioid user who has used opioids for nontherapeutic (recreational) purposes on at least 10 occasions within their lifetime, with at least 1 opioid use in the last 90 days.

4. Participant has a body mass index (BMI) range of 18 to 36 kg/m², inclusive and weighs at least 50 kg at screening.
5. Female participant is not pregnant (see [Section 10.2 Appendix 2 Contraception Requirements]) and at least 1 of the following conditions apply:
 - a. Not a woman of childbearing potential (WOCBP) (see [Section 10.2 Appendix 2 Contraception Requirements])
 - b. WOCBP who agrees to follow the contraceptive guidance (see [Section 10.2 Appendix 2 Contraception Requirements]) from the time of informed consent through at least 28 days after final IP administration.
6. Female participant must agree not to breastfeed starting at screening and throughout the study period and for 28 days after final IP administration.
7. Female participant must not donate ova starting at first dose of IP and throughout the study period and for 28 days after final IP administration.
8. Male participant with female partner(s) of childbearing potential (including breastfeeding partner[s]) must agree to use contraception (see [Section 10.2 Appendix 2 Contraception Requirements]), throughout the treatment period and for 90 days after final IP administration.
9. Male participant must not donate sperm during the treatment period and for 90 days after final IP administration.
10. Male participant with a pregnant partner(s) must agree to remain abstinent or use a condom with spermicide for the duration of the pregnancy throughout the study period and for 90 days after final IP administration.
11. Participant agrees to not participate in another interventional study while participating in the present study.
12. Participant must be willing to abstain from smoking (including use of tobacco-containing products and nicotine or nicotine-containing products [e.g., electronic vapes]) from at least 1 hour predose through at least 8 hours postdose on days 9 and 10.

5.2 Exclusion Criteria

Participant will be excluded from participation in the study if any of the following apply:

1. Participant has received any investigational therapy within 28 days or 5 half-lives, whichever is longer, prior to screening.
2. Participant has any condition which, in an investigator's opinion, makes the participant unsuitable for study participation.
3. Female participant who has been pregnant within 6 months prior to screening or breastfeeding within 3 months prior to screening.
4. Participant has a known or suspected hypersensitivity to ASP8062 or morphine and/or other opioids, or any components of the formulations used.
5. Participant has had previous exposure with ASP8062.
6. Participant has any of the liver function tests (alkaline phosphatase [ALP], alanine aminotransferase [ALT], aspartate aminotransferase [AST], gamma-glutamyl transferase

and total bilirubin [TBL]) $\geq 1.5 \times$ upper limit of normal (ULN) on day -1. In such a case, the assessment may be repeated once.

7. Participant has any clinically significant history of allergic conditions (including drug allergies, asthma or anaphylactic reactions, but excluding untreated, asymptomatic, seasonal allergies) prior to first IP administration as judged by an investigator.
8. Participant has any history or evidence of any clinically significant cardiovascular, gastrointestinal, endocrinologic, hematologic, hepatic, immunologic, metabolic, urologic, pulmonary, neurologic, dermatologic, renal and/or other major disease or malignancy, as judged by an investigator, with exception of history of cholecystectomy.
9. Participant has a history of moderate or severe use disorder for any substance other than caffeine or tobacco (based on the DSM-5 criteria).
10. Participant has a history or presence of any clinically significant psychiatric disorders such as, bipolar 1, schizophrenia, schizoaffective disorder or major depressive disorders, as judged by an investigator.
11. Participant has had recent suicidal ideation within the last 12 months or participant who is at significant risk to commit suicide, as judged by an investigator, using the Baseline/Screening Columbia-suicide severity rating scale (C-SSRS) at screening and the Since Last Visit C-SSRS on day -1.
12. Participant has/had febrile illness or symptomatic, viral, bacterial (including upper respiratory infection) or fungal (noncutaneous) infection within 1 week prior to day -1.
13. Participant has any clinically significant abnormality following an investigator's review of the physical examination, ECG and protocol-defined clinical laboratory tests at screening or on day -1.
14. Participant has a mean pulse < 50 or > 90 bpm; mean systolic blood pressure > 150 mmHg; mean diastolic blood pressure > 95 mmHg (measurements taken in duplicate after participant has been resting in the supine position for at least 5 minutes) on day -1. If the mean blood pressure exceeds the limits above, 1 additional duplicate may be taken.
15. Participant has a mean corrected QT interval using Fridericia's formula (QTcF) of > 450 msec (for male participants) and > 470 msec (for female participants) on day -1. If the mean QTcF exceeds the limits above, 1 additional triplicate ECG may be taken.
16. Participant has a positive test for amphetamines, barbiturates, benzodiazepines, cocaine, phencyclidine, alcohol and/or opiates on day -1. Positive tetrahydrocannabinol is not exclusionary and a cannabis intoxication evaluation will be performed. Participant may be reconsidered at an investigator's discretion.
17. Participant has used any prescribed or nonprescribed drugs (including vitamins and natural and herbal remedies, e.g., St. John's Wort) in the 2 weeks prior to first IP administration, except for occasional use of acetaminophen (up to 2 g/day), topical dermatological products, including corticosteroid products, hormonal contraceptives and hormone replacement therapy (HRT).
18. Criterion Removed.

19. Participant has used any inducer of CYP3A4-related metabolism (e.g., barbiturates, rifampin, apalutamide, carbamazepine, enzalutamide, mitotane, phenytoin, St. John's wort, bosentan, efavirenz, etravirine, phenobarbital, primidone, armodafinil, modafinil, and rufinamide) in the 3 months prior to day -1.
20. Participant has had significant blood loss, donated approximately 500 mL of whole blood (excluding plasma donation) within 56 days prior to screening or donated plasma within 7 days prior to day -1.
21. Participant has a positive serology test for hepatitis B surface antigen, hepatitis C virus antibodies or antibodies to HIV type 1 and/or type 2 at screening.
22. Participant has loss of ability to freely provide consent through imprisonment or involuntary incarceration for treatment of either a psychiatric or physical (e.g., infectious disease) illness.
23. Participant is an employee of Astellas, the study-related contract research organizations (CROs) or the clinical unit.

5.3 Lifestyle Considerations

5.3.1 Exercise

Participants will refrain from strenuous exercise from 48 hours prior to admission to the clinical unit up to and including the ESV.

Participants are encouraged to walk and stretch during the confinement period to avoid AEs associated with the sedentary environment.

5.3.2 Dietary and Fluid Restrictions

To avoid false positive results of the drugs of abuse test, no food or drinks containing poppy seeds (e.g., specialty breads and muffins) will be allowed from 48 hours prior to admission to the clinical unit up to and including the ESV.

Participants will not be allowed to consume food and drinks which may interact with circulatory, gastrointestinal, liver or renal function from at least 24 hours for alcohol or xanthine-containing products (including caffeine) and 72 hours for grapefruit/Seville orange or grapefruit/Seville orange-containing products prior to admission to the clinical unit up to and including the ESV.

Participants will be served normal balanced caloric drinks and meals at consistent times during their stay in the clinical unit. Total daily caloric intake will preferably not exceed normal daily limits (approximately 2800 kcal/male and female participants). Dietary and fluid restrictions apply to dosing conditions as specified in [Section 6.1] Investigational Product(s)]. The menu and nutritional information will be documented in the clinical study file.

Standardized lunch and dinner will be served at fixed time points on day 1. On other days, the participants will receive standard meals.

5.3.3 Smoking Restrictions

Participants will not be allowed to smoke (including using tobacco-containing products and nicotine or nicotine-containing products [e.g., electronic vapes]) from at least 1 hour predose through at least 8 hours postdose on days 9 and 10 during measurements for continuous pulse oximetry and end tidal CO₂.

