18. On days 1, 9 and 10, ASP8062 or placebo will be administered orally under fasting conditions (i.e., no food or beverage will be allowed from at least 10 hours predose through at least 4 hours postdose) with approximately 240 mL water. Water intake will be prohibited from at least 1 hour predose through at least 1 hour postdose, except for the approximately 240 mL water to swallow the investigational product. On all other dosing days, ASP8062 or placebo will be administered orally under standardized fed conditions (i.e., meals will be served up to 1 hour predose or at least 2 hours postdose) with approximately 240 mL water. Water intake will be allowed ad libitum.
19. On day 10, morphine will be administered as a single oral dose under existing fasting conditions with approximately 240 mL water, immediately after the ASP8062 or placebo dose. Water intake will be prohibited from at least 1 hour predose through at least 1 hour postdose, except for the approximately 240 mL water to swallow the investigational product.

Table 2 Sample Collection Schedule

Day	Time Point	Pharmacokinetics ASP8062/metabolites	Pharmacokinetics Morphine/metabolites	Vital Signs	Clinical Laboratory Tests	12-lead ECG	ARCI-49	Spot End Tidal CO ₂	Spot SpO ₂
Days -28 to -2	Screening			X	X	X			
-1				X	X	X			
1	Predose			X	X	X	X		X
	2 hours								
2	Predose								
	2 hours								
3	Predose			X	X				
	2 hours								
4	Predose								
	2 hours								
5	Predose								
	2 hours								
6	Predose			X	X				
	2 hours								
7	Predose								
	2 hours								
8	Predose								
	2 hours								

Table continued on next page

Day	Time Point	Pharmacokinetics ASP8062/metabolites	Pharmacokinetics Morphine/metabolites	Vital Signs	Clinical Laboratory Tests	12-lead ECG	ARCI-49	Spot End Tidal CO ₂	Spot SpO ₂
9	Predose	X		X	X	X	X	X	X
	0.25 hour	X							
	0.5 hour	X							
	1 hour	X		X				X	X
	1.5 hours	X							
	2 hours	X		X	X	X	X	X	X
	2.5 hours	X							
	3 hours	X							
	4 hours	X		X		X	X	X	X
	6 hours	X							
	8 hours	X		X			X	X	X
	12 hours	X		X		X	X		X
	16 hours	X							
10	Predose	X	X	X	X	X	X	X	X
	0.25 hour	X	X						
	0.5 hour	X	X						
	1 hour	X	X	X				X	X
	1.5 hours	X	X						
	2 hours	X	X	X	X	X	X	X	X
	2.5 hours	X							
	3 hours	X	X						
	4 hours	X	X	X		X	X	X	X

Table continued on next page

Day	Time Point	Pharmacokinetics ASP8062/metabolites	Pharmacokinetics Morphine/metabolites	Vital Signs	Clinical Laboratory Tests	12-lead ECG	ARCI-49	Spot End Tidal CO ₂	Spot SpO ₂
10	6 hours	X							

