9.4 Statistical Analyses

9.4.1 General Considerations

In general, data will be summarized with descriptive statistics for continuous endpoints, and frequency and percentage for categorical endpoints, unless otherwise specified. Percentages by categories will be based on the number of participants with no missing data (i.e., will add up to 100%).

Baseline will be defined as the last nonmissing observation prior to first administration of IP, unless otherwise specified.

Demographics and baseline characteristics (age, sex, race, ethnicity, body weight, height and BMI) will be summarized by treatment group and overall for all randomized participants.

The number and percentage of participants who completed and discontinued treatment and reasons for treatment discontinuation will be presented for all randomized participants and for participants in the safety analysis set (SAF) by treatment group (ASP8062 alone, placebo alone, morphine in combination with ASP8062, morphine in combination with placebo) and overall. Similar tables for screening disposition, investigational period disposition and follow-up disposition will also be presented for all randomized participants by treatment group (ASP8062 alone, placebo alone, morphine in combination with ASP8062, morphine in combination with placebo) and overall. All disposition details and dates of first and last evaluations for each participant will be listed.

Previous and concomitant treatment (medication and nonmedication therapy) and medical history will be listed. The number and percentage of participants exposed to IP will be summarized by treatment group (ASP8062 alone, placebo alone, morphine in combination with ASP8062, morphine in combination with placebo) and visit. All IP exposure data will be listed.

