9.4.3.4 Continuous Pulse Oximetry and Spot Blood Oxygen Saturation

The spot SpO₂ levels and change from baseline (day 1) will be listed and summarized by treatment group and time point. The number and percentage of participants with SpO₂ levels

as per [Table 8] at any time point will be summarized by treatment group. The lowest SpO₂ level across the time points will be used in the analysis.

Table 8 Criteria for Assessing Spot Blood Oxygen Saturation

Parameter	Criteria
SpO ₂ level (%)	< 90, < 92, < 94, < 96

SpO₂: blood oxygen saturation

The number and percentage of participants who reach an alarm value of continuous pulse oximetry, and the number of times an alarm value was reached will be listed and summarized by treatment.

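### Spot SpO2 and vital-sign changes on days 9 and 10 are measured from a day 1 baseline with no smoking restriction, so within-group changes can include a smoking-related shift; the contrast with placebo is not systematically biased.

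*Combined protocol and SAP*

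**What the plan says.** **Smoking rule.** Section 5.3.3 applies it "from at least 1 hour predose through at least 8 hours postdose on days 9 and 10 during measurements for continuous pulse oximetry"; the same window covers end tidal CO2. Inclusion criterion 12 repeats it for eligibility: "Participant must be willing to abstain from smoking", with the same window, "through at least 8 hours postdose on days 9 and 10". Neither place mentions day 1.

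**Smokers are eligible.** No criterion excludes them, and the substance-use exclusion exempts tobacco: "Participant has a history of moderate or severe use disorder for any substance other than caffeine or tobacco".

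**Baselines.** For spot SpO2, section 9.4.3.4 says "change from baseline (day 1) will be listed and summarized by treatment group and time point". For blood pressure, pulse and respiratory rate the general rule in 9.4.1 applies: "Baseline will be defined as the last nonmissing observation prior to first administration of IP, unless otherwise specified". Table 2 schedules both SpO2 and vital signs at day 1 predose, as single measurements (Table 1, footnotes 10 and 14). Spot end tidal CO2 takes its baseline on day 9 (9.4.3.8).

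**Other conditions on day 1.** Table 1, footnote 18, gives days 1, 9 and 10 the same fasting rule: "no food or beverage will be allowed from at least 10 hours predose through at least 4 hours postdose". Smoking is not part of it.

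**Analysis.** Section 9.1 states no hypotheses. Sections 9.4.3.3 and 9.4.3.4 summarize results and changes descriptively by treatment group and time point. Smoking status is not among the baseline characteristics listed in 9.4.1.

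**The concern.** By tying the smoking rule to the oximetry and end tidal CO2 measurements, the protocol itself treats smoking as relevant to them. Fasting conditions are matched across days 1, 9 and 10, and the end tidal CO2 baseline lies on a restricted day. The spot SpO2 and vital-sign baseline lies outside the restriction. Nonsubstantial Amendment 1 records that the SpO2 baseline moved from day 9 to day 1, which may explain how this arose, but the point rests on the current text alone.

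SpO2, blood pressure, pulse and respiratory rate are all primary safety measures. If some participants smoke shortly before a single baseline reading and abstain before the later ones, part of the reported within-group change reflects smoking conditions and not ASP8062 or morphine. Because the planned outputs are within-group summaries and smoking status is not tabulated, a reader could not see how much.

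**Working it through.** The plan states no figure on this point, so there is nothing to reproduce. The check sets the rules side by side and then sizes what could follow.

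**Step 1: smoking rule at each reading (Table 2 against 5.3.3)**

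| Reading | Smoking rule |
|---|---|
| Day 1 predose SpO2 and vital signs (baseline) | none |
| Days 9 and 10, predose to 8 h | restricted |
| Days 9 and 10, 12 h | not guaranteed |
| Vital signs, days 3, 6 and 11 to 16 | none |
| End tidal CO2 baseline (day 9) and later readings to 8 h | restricted |

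The mismatch is therefore confined to changes from day 1 to the day 9 and 10 readings up to 8 h. For vital signs on days 3, 6 and 11 to 16, baseline and reading both have no rule.

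**Step 2: which summaries use the day 1 baseline**

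Only the change scores for spot SpO2 and vital signs. Tables 7 and 8 count absolute values, as do the alarm summaries. Day 10 versus day 9 compares two restricted days up to 8 h.

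**Step 3: size**

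Let p be the share of participants who smoke shortly before the day 1 reading, and d the resulting difference in that reading. The documents give neither.

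- Within-group shift: p × d in size, expected equally in both arms.
- Bias in ASP8062 minus placebo: expected value 0; SD = d × √[p(1 − p)(1/nA + 1/nP)].

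About 24 participants at 2:1 (9.2 and 6.3.6.2) gives 16 versus 8; the minimum of 18 completers gives 12 versus 6 if the ratio holds. With 1/16 + 1/8 = 0.1875 and 1/12 + 1/6 = 0.25:

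| Assumed p | SD at 16:8 | SD at 12:6 |
|---|---|---|
| 0.5 | √(0.25 × 0.1875) = 0.217 d | √(0.25 × 0.25) = 0.250 d |
| 0.8 | √(0.16 × 0.1875) = 0.173 d | √(0.16 × 0.25) = 0.200 d |

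Exact binomial sums give the chance that the arms differ by 25 percentage points or more in smoker share. For p = 0.25 or 0.75 it is 24% at 16:8 and 34% at 12:6; for p = 0.5 it is 32% and 41%.

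**Step 4: illustration only**

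Assume d of 0.5 to 1 SpO2 point and 5 to 10 bpm for pulse, p of 0.5 to 0.8, and every smoker smoking just before the baseline reading (a worst case).

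- Within group: SpO2 0.5 × 0.5 = 0.25 to 0.8 × 1 = 0.8 points; pulse 0.5 × 5 = 2.5 to 0.8 × 10 = 8 bpm.
- Between-arm SD at 16:8: SpO2 0.173 × 0.5 = 0.09 to 0.217 × 1 = 0.22 points; pulse 0.173 × 5 = 0.9 to 0.217 × 10 = 2.2 bpm.

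The steps in Table 8 are 2 SpO2 points. No value is assumed for blood pressure or respiratory rate.

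**The case against.** A reader might infer that the change scores confound drug effect with smoking, so that the apparent effect of ASP8062 is biased. The documents do not support that. The study is randomized and placebo-controlled, both arms follow the same smoking rules on the same days, and safety is summarized by treatment group. The placebo group carries the same expected shift. What remains is chance imbalance, as with any unstratified covariate in a descriptive study of 24. The measure the protocol singles out as sensitive, end tidal CO2, is untouched, and day 9 predose readings already offer a baseline taken on a restricted day. All of this stands.

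It can also be said that smoking just before the day 1 reading is conjecture. Participants are resident from day -1, and vital signs follow at least 5 minutes of supine rest. The documents neither permit nor forbid smoking in the unit at that time. That is right, and it is why the size is unknown; it does not remove the mismatch in the rules.

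Finally, restricting day 1 would leave vital signs on unrestricted days no longer matched to baseline. That also stands, and it counts as a cost of the fix. It weighs least for spot SpO2, which is scheduled only on days 1, 9 and 10.

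The appeal to placebo does not answer everything. No between-arm estimate is specified for these change scores, so the tabulated result is the within-group change, which carries the full shift.

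**Conclusion.** The point holds in a narrow form. Within-group changes in spot SpO2, blood pressure, pulse and respiratory rate from day 1 to days 9 and 10, up to 8 h, compare readings taken under different smoking rules and can include a smoking-related shift of p × d. Both factors are unknown, so the ranges above show scale and are not estimates. The ASP8062-versus-placebo contrast has zero expected bias from this source. Its chance component has an SD of about 0.17 to 0.22 times the acute effect at 16 versus 8, for an assumed smoker share of 50% to 80%. The severity is low: a cheap improvement, not a threat to the study's conclusions.

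**What to change.** In section 5.3.3 and inclusion criterion 12, add day 1: no smoking or nicotine for at least 1 hour before the predose SpO2 and vital-sign readings, and until they are complete. The rule should be tied to the readings and not to the dose. Section 7.2.9 allows predose procedures up to 60 minutes before dosing, so a rule starting 1 hour predose could still allow a cigarette minutes before the baseline value.

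Costs:

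- A short abstinence on day 1 for resident participants.
- Vital signs on days 3, 6 and 11 to 16, and readings at 12 h on days 9 and 10, would not be matched to the restricted baseline; those changes should be read against placebo.
- The match on days 9 and 10 is to the rule and not to the length of abstinence: the 8 h reading follows at least 9 hours without smoking (1 h predose plus 8 h), the baseline at least 1 hour.

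Adding smoking status to the baseline characteristics in 9.4.1 would let a reader see any imbalance between the arms.
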